6.3 Significance Levels

Two-sided hypothesis testing will be applied to test the statistical significance, and multiple testing adjustment for controlling error rates will not be applied. A p-value of <0.05 will be considered statistically significant. SAS for Windows Version 9.4 will be used for all statistical analyses.

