Mixed linear model will be used to evaluate factors associated with HbA1c level in the pre- and post-index periods among U-500R syringe initiators, U-500R Kwikpen initiators, and U-500R device switchers. Mixed linear model is used for studies with a longitudinal feature in which a continuous outcome variable is measured for the same subject repeatedly over the time period. Based on the distribution of the data, observations measured for the same subject are likely to be correlated over the study period and these data are considered as "multilevel" data. In addition, mixed linear model has a mixed effect consisting both fixed and random effects. For this objective, mixed linear model helps to evaluate the effect of both time varying and time-independent variables on the HbA1c, while taking into account for correlation due to multiple assessments from the same individual. In the current model, HbA1c level which is measured at two time intervals (before and after the index event; U-500R initiation/device switch), will be considered the dependent variable. Observed TDD will be considered as the time varying covariate in the model (measured both before and after the index event), and the time independent covariates include the demographic and clinical characteristics.

The complete list of covariates will include:

- age
- sex
- race
- BMI
- baseline CCI score
- observed TDD from claims
- time (pre/post)

Note: Age, sex, race, BMI, and CCI score will be assessed during pre-index period. Observed TDD will be calculated during the entire pre-index and post-index periods, respectively. Pre-index

[2018-7241 Study Identifier] Observational Study Protocol

HbA1c will be defined as the HbA1c measurement -90/+30 days of the index date. For patients with multiple HbA1c measurements within this period, the measurement taken closest to the index event date will be reported as the pre-index HbA1c value. Post-index HbA1c will be defined as the HbA1c within 2 months of the end of the follow-up period.

Adherence will not be included as one of the covariates here due to the high collinearity between time and adherence. Hence, further mediation analysis will be performed to determine the mediator effect of adherence on HbA1c.

Mediation Analysis:

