Mediation analysis following the Baron and Kenny's steps will be considered to understand the impact of index event (time: pre-index indicates use of othe insulin and post-index indicates U-500R use) on HbA1c through potential mediators. Adherence is considered as a potential mediator between the HbA1c and time. The key steps in mediation analysis include a model of the mediator (adherence) as a function of the predictor (time) and a model of the outcome (HbA1c) as a function of both the mediator (adherence) and the predictor (time). Bootstrapping method will be used to test the effect of mediator. The detailed steps are described below:

Step 1: Effect of predictor (time) on the outcome (HbA1c):

In the first step, the effect of time on the dependent variable HbA1c will be assessed. Statistically, a significant relationship between the two variables will trigger the next step of the mediation analysis. However, it is suggested that the clinical significance and theoretical evidence should be considered in the case of failure to detect an association that is statistically significant. Since the effect of time on HbA1c is the primary interest of this analysis, we will carry out the next step regardless of the significance between time and HbA1c.

Step 2: Effect of predictor (time) on the mediator (adherence):

The effect of time (predictor) on the hypothesized mediator adherence will be assessed, and adherence will be considered as a dependent variable in the model. Potential mediation effect will be supported by a statistically significant relationship between time and adherence, which will lead to the next step of the analysis.

Step 3: Combined effect of predictor (time) and mediator (adherence) on the outcome (HbA1c):

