Adherence will be included and adjusted as a covariate in the model assessing the relationship between time (predictor) and the dependent variable HbA1c. Evidence of a mediation effect will be strengthened if the relationship between time and HbA1c disappears or weakens while adjusting for adherence. If the effect of time on HbA1c became insignificant, this indicates that the relationship between time and HbA1c is fully mediated by adherence (full mediation); and if the relationship remains significant with a reduced magnitude, this indicates that adherence is partially meditating the relationship between time and HbA1c (partial mediation). If any of the mediation effect exists, the next step will be used to further test the significance of the mediation effect.

[2018-7241 Study Identifier] Observational Study Protocol

Step 4: Assess the statistical significance of the effect of the mediator (adherence):

Bootstrapping method will be applied to evaluate the statistical significance of the adherence. At least 500 bootstrapping sample will be applied. All estimates will be combined in one dataset to compute the indirect, direct and total effects. The summary of effects table along with the bootstrap estimates and p-values will be provided. If the p-value of the indirect effect is significant, this clearly indicates that the mediation effect is significant. Additionally, the direct effect of time on the outcome HbA1c, as well as the total effect, which is a sum of the indirect and direct effect and the percentage mediated will be provided.

Research Objective 2: Secondary Objective 2aDescriptive Analysis

Number of hypoglycemia events will be analyzed descriptively before and after U-500R syringe initiation and U-500R Kwikpen initiation, and before and after U-500R device switch from syringe to Kwikpen.

Numbers and percentages will be provided for dichotomous and polychotomous variables. Means and standard deviations (SDs) will be provided for continuous variables. McNemar's test will be used to determine statistical significance of before and after values for categorical variables, and the paired t-test will be used to assess the statistical significance of before and after values in continuous variables.

Multivariate Analysis: Hypoglycemia Event

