[2018-7241 Study Identifier] Observational Study Protocol*Step 1: Effect of predictor (time) on the outcome (costs):*

In the first, the effect of time on the dependent variable costs will be assessed. Statistically, a significant relationship between the two variables will trigger the next step of the mediation analysis. However, it is suggested that the clinical significance and theoretical evidence should be considered in the case of failure to detect an association that is statistically significant. Since the effect of time on costs is the primary interest of this analysis, we will carry out the next step regardless of the significance between time and costs.

Step 2: Effect of predictor (time) on the mediator (adherence):

The effect of time (predictor) on the hypothesized mediator adherence will be assessed, and adherence will be considered as a dependent variable in the model. Potential mediation effect will be supported by a statistically significant relationship between time and adherence, which will lead to the next step of the analysis.

Step 3: Combined effect of predictor (time) and mediator (adherence) on the outcome (costs):

Adherence will be included and adjusted as a covariate in the model assessing the relationship between time (predictor) and the dependent variable costs. Evidence of a mediation effect will be strengthened if the relationship between time and costs disappears or weakens while adjusting for adherence. If the effect of time on costs became insignificant, this indicates that the relationship between time and costs is fully mediated by adherence (full mediation); and if the relationship remains significant with a reduced magnitude, this indicates that adherence is partially mediating the relationship between time and costs (partial mediation). If any of the mediation effect exists, the next step will be used to further test the significance of the mediation effect.

Step 4: Assess the statistical significance of the effect of the mediator (adherence):

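### The mediation rule for HbA1c and for costs infers full mediation from a non-significant time effect, so partial mediation can be labelled full when power is low or collinearity is high

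*Protocol*

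**What the plan says.** All of this is in Protocol section 6.4.1 unless stated.

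- **Covariate models for HbA1c and for costs.** Adherence is kept out and moved to a mediation analysis: "Adherence will not be included as one of the covariates here due to the high collinearity between time and adherence". The sentence appears in both sections. No correlation or VIF is given.
- **Step 1 (total effect).** A significant effect of time is not needed to go on: "we will carry out the next step regardless of the significance between time and HbA1c". The cost section says the same.
- **Step 2 (time on adherence).** "Potential mediation effect will be supported by a statistically significant relationship between time and adherence, which will lead to the next step".
- **Step 3 (time and adherence together).** "If the effect of time on HbA1c became insignificant, this indicates that the relationship between time and HbA1c is fully mediated by adherence". A time effect that stays significant but shrinks is called partial mediation. The next step is used if either kind is found. For costs: "If the effect of time on costs became insignificant, this indicates that the relationship between time and costs is fully mediated by adherence".
- **Step 4.** The indirect effect is tested by bootstrap (at least 500 samples for HbA1c). The direct, indirect and total effects and the percentage mediated are reported.
- **Section 6.3.** Tests are two-sided. "A p-value of <0.05 will be considered statistically significant", and "multiple testing adjustment for controlling error rates will not be applied".

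**The concern.** Step 3 treats failure to reject as evidence that the direct effect is absent. Full mediation is a claim that the direct effect is zero or negligible, and a p-value of 0.05 or more cannot establish that. The inference is made in a model containing the two variables that the protocol had just separated for high collinearity. If that description is right, the standard error of time is larger in Step 3 than in Step 1, and the time effect can lose significance even if the coefficient hardly moves. Because Step 1 does not require a significant total effect, the rule can also be applied where no effect of time was established.

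Whether adherence played a role in HbA1c change is a named bullet of Primary Objective 2 (section 4.1). The relation of adherence to costs belongs to Primary Objective 3. HbA1c is analysed in three cohorts in VHA, LCED and pooled data (Table 1), so the same underlying effect could be called full in a small data set and partial in a large one.

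**Working it through.** The protocol states no effect size, SD, power or time-adherence correlation for this analysis, so there is no figure to reproduce.

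**Inputs.** From the documents: two-sided 0.05 (6.3), and VHA counts before selection with at least two HbA1c values of 4,066 (Kwikpen) and 5,718 (vial) (Table 4). Assumed: total effect 0.5 HbA1c points, half of it direct (0.25), SD s = 1.5 for the paired change, n = 200, 500 or 2,000, and VIF about 1.1, 2 or 5.

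**Formula.** With one pre and one post record per patient, regress the change in HbA1c on the change in adherence. The intercept is the direct effect of time, with

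SE = (s/√n) × √(1 + d²),

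where d is the mean change in adherence divided by its SD. VIF = 1 + d², so d = 0.3, 1, 2 gives 1.09, 2, 5. This simplifies the planned mixed model. Then

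P(not significant) = Φ(1.96 − 0.25/SE) − Φ(−1.96 − 0.25/SE).

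Example, n=200, VIF 2: SE = 1.5/14.14 × 1.414 = 0.150; 0.25/0.150 = 1.667; probability 0.62.

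**Step 3 alone: chance that a real direct effect is non-significant**

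| n | VIF 1.1 | VIF 2 | VIF 5 |
|---|---|---|---|
| 200 | 38% | 62% | 82% |
| 500 | 5% | 25% | 62% |
| 2,000 | about 0% | about 0% | 8.5% |
| 4,066 | about 0% | about 0% | 0.3% |

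At n=200 with no collinearity (d=0) the figure is already 35%, so low power alone can trigger the label.

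**Adding Step 4.** Simulating the same scenario, with a Monte Carlo interval in place of the bootstrap and a significant indirect effect also required: at n=200 the 82% falls to about 22%, the 62% to roughly half, and the 38% barely changes. At n=500 and VIF 5, the 62% falls to about 43–45%.

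**What Step 4 does and does not repair.** A second simulation used paired differences, n=200, 90% power for the total effect, 500 bootstraps, and results conditional on a significant total effect. Here r is the time-adherence correlation and VIF = 1/(1 − r²).

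- *No true mediation.* Full mediation is declared at Step 3 in 12%, 30%, 48% and 68% of runs for r = 0.5, 0.7, 0.8 and 0.9. With Step 4 also required, this falls to 1.4%, 2.6%, 3.3% and 3.8%.
- *30% truly mediated.* Of runs that pass Steps 3 and 4, 63% (r = 0.5) and about 95% (r = 0.7) carry the label full.
- *50% truly mediated.* The corresponding figures are 74% and 96%.

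**Sensitivity to effect size.** At r = 0.8, a direct effect of 0.2 SD of the paired difference is non-significant in 60% of cases at n=200, 24% at n=500, 3% at n=1,000 and about 0% at n=4,066. A direct effect of 0.05 SD (0.05 × 1.5 = 0.075 HbA1c points) is still non-significant in 52% at n=4,066.

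**The case against.** A reader might infer three stronger things that the documents do not support.

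1. *That the protocol admits the joint model is too collinear to fit.* It says only that collinearity is high, as the reason to leave adherence out of one model. Correlation short of 1 makes estimates imprecise, not impossible. A VIF of 5 would need a mean change in adherence twice its SD, and nothing in the protocol shows that.
2. *That loss of power alone would be reported as proof that adherence explains everything.* Step 4 tests the indirect effect and reports the direct effect and percentage mediated. Where there is no mediation, the second simulation shows it stops nearly all false claims. What survives is narrower: a full label can stand beside a percentage mediated that contradicts it, and the protocol does not say which governs.
3. *That the bootstrap test may never be run.* If time does not move adherence, there is little indirect effect to test. Step 3 opens the gate for any weakening of the time effect. The gate closes mainly when adherence and the direct effect act in opposite directions, so that adjustment enlarges the time effect. That case is real but limited.

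It is also fair that sizes of 200 and 500 are assumed, that the only counts given are far larger, and that no LCED or switcher count is stated. The before/after comparisons and covariate models do not depend on this rule. These points lower the severity. They do not make non-significance evidence of a zero direct effect.

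**Conclusion.** The rule is wrong as written in both mediation sections: full versus partial is decided by whether time keeps its significance, and Step 4 does not correct that decision. The error to expect is partial mediation reported as full.

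Its size rests on quantities the protocol does not give. Under the stated assumptions it is substantial at a few hundred patients and negligible at the VHA counts before selection. Requiring Step 4 lowers the high-VIF figures most. It therefore matters mainly where a cohort is small after selection or the true direct effect is small. Should fix: the point affects the interpretation of named parts of Primary Objectives 2 and 3, not the main before/after results.

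**What to change.** In both mediation sections:

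- Delete the full/partial classification based on significance, and the significance gates at Steps 2 and 3.
- Always estimate the indirect effect, the direct effect and the percentage mediated, each with a 95% bootstrap confidence interval, resampling patients with both of their records.
- Base the conclusion on the indirect effect and its interval. The interval for the direct effect then shows how much is left unexplained.
- Replace the advance statement of high collinearity with a reported VIF or correlation, so that excluding adherence from one model and including it in the other are consistent.

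The cost is a change of wording. The bootstrap and the effect estimates are already planned, and the resampling detail can sit in the SAP.

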Bootstrapping method will be applied to evaluate the statistical significance of the adherence. The summary of effects table along with the bootstrap estimates and p-values will be provided. If the p-value of the indirect effect is significant, this clearly indicates that the mediation effect is significant. Additionally, the direct effect of time on the outcome costs, as well as the total effect, which is a sum of the indirect and direct effect and the percentage mediated will be provided.

7. Safety Evaluations

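### The minimum of 500 bootstrap samples for the HbA1c mediation test is low for a 0.05 decision: a borderline verdict could turn on the random seed

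*Protocol*

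**What the plan says.** Protocol 6.4.1 sets out a four-step mediation analysis twice: for HbA1c under Primary Objective 2 and for costs under Primary Objective 3. Adherence is the proposed mediator in both.

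For HbA1c, Step 4 says: "At least 500 bootstrapping sample will be applied". On output it promises that "The summary of effects table along with the bootstrap estimates and p-values will be provided". The decision rule is: "If the p-value of the indirect effect is significant, this clearly indicates that the mediation effect is significant".

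Section 6.3 supplies the threshold: "Two-sided hypothesis testing will be applied to test the statistical significance", and "A p-value of <0.05 will be considered statistically significant". It adds that "multiple testing adjustment for controlling error rates will not be applied".

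For costs, Step 4 uses the same method ("Bootstrapping method will be applied to evaluate the statistical significance of the adherence") and the same decision rule, but gives no number of samples.

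Neither Step 4 says how the p-value is computed from the bootstrap replicates.

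**The concern.** A bootstrap p-value is itself estimated by simulation. With few replicates, two runs on the same data can report different values. That is harmless when the p-value is far from the threshold. Close to 0.05, however, the declaration of mediation can depend on which random seed was used.

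The step is not peripheral. Primary Objective 2 asks whether adherence played a role in the HbA1c change, and adherence is left out of the HbA1c mixed model because of its collinearity with time. The mediation analysis is therefore where that question gets its formal test. Table 1 lists three cohorts and three data sets for Primary Objective 2, so up to 3 × 3 = 9 HbA1c tests could reach Step 4, without multiplicity adjustment. Some of them overlap, because the pooled data contain the other two data sets. With several verdicts, one near 0.05 is plausible, though nothing in the protocol shows that one will occur.

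**Working it through.** The protocol gives no derivation or precision target for 500, so there is no figure to reproduce. The check is how much simulation error 500 replicates leave.

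**Inputs**
- Number of samples B: at least 500 (6.4.1, Primary Objective 2, Step 4). The check uses B = 500, the smallest number that complies.
- Threshold: two-sided 0.05 (6.3).
- How p is formed: not stated. Three forms are taken as assumptions.

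Below, the true p is the value that would be reached with unlimited replicates.

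**Noise at a true p of 0.05, B = 500**

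1. Percentile p, twice the smaller tail share. The tail share is 0.025.
 - SE = 2 × √(0.025 × 0.975 / 500) = 0.0140.
 - The binomial 2.5% and 97.5% points of the tail count are 6 and 20. The 95% range of p is 2 × 6/500 = 0.024 to 2 × 20/500 = 0.080.
2. A single share, with both tails counted together.
 - SE = √(0.05 × 0.95 / 500) = 0.0097.
 - 95% range: 0.05 ± 1.96 × 0.0097, about 0.031 to 0.069.
3. Normal-theory p from the bootstrap standard error, assuming roughly normal replicates.
 - The relative error of that standard error is 1/√(2 × 500) = 0.0316.
 - z runs over 1.96 × (1 ± 1.96 × 0.0316), about 1.84 to 2.08. The range of p is about 0.037 to 0.066.

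**Chance that the reported p falls on the wrong side of 0.05, B = 500**

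Under form 1, p < 0.05 requires a tail count of 12 or fewer, and the chance is exact binomial. Under form 3 it is Φ of −|z_true/1.96 − 1| / 0.0316.

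| True p | Form 1 (percentile) | Form 3 (bootstrap SE) |
|---|---|---|
| 0.02 | 0.2% | under 0.1% |
| 0.03 | 4.1% | under 0.1% |
| 0.04 | 21% | 6.5% |
| 0.06 | 26% | 10% |
| 0.07 | 11% | 0.8% |
| 0.08 | 3.6% | under 0.1% |
| 0.10 | 0.3% | under 0.1% |

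If s is the chance of a significant result, two runs with different seeds disagree with probability 2s(1 − s). Under form 1 this is 2 × 0.207 × 0.793 = 33% at a true p of 0.04, and 2 × 0.264 × 0.736 = 39% at 0.06.

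**What more samples buy (form 1)**

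| B | SE at true p 0.05 | 95% range | Wrong side at 0.04 | Wrong side at 0.06 |
|---|---|---|---|---|
| 500 | 0.0140 | 0.024–0.080 | 21% | 26% |
| 1,000 | 0.0099 | 0.032–0.070 | 16% | 15% |
| 5,000 | 0.0044 | 0.042–0.059 | 0.8% | 1.5% |
| 10,000 | 0.0031 | 0.044–0.056 | under 0.1% | 0.1% |

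An SE of 0.005 needs B = 4 × 0.025 × 0.975 / 0.005² = 3,900.

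**The case against.** The strongest reply is that 500 is a floor. An analyst who runs 5,000 or 10,000 samples complies fully. That is right: a reader might infer that the plan commits itself to a noisy p-value, and the text does not support this. What remains is that the floor is the only guarantee the protocol gives, and a run at exactly 500 would meet it.

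Second, the p-value method is open, and under the bootstrap-standard-error form the noise is clearly smaller. This also stands, and it is why the size is given as a range.

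Third, the affected band is narrow, and the protocol gives no reason to expect indirect effects in it. That limits the importance of the point without removing it.

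Fourth, a reader might infer that the whole mediation conclusion hangs on this p-value. It does not. Step 2 looks for an effect of time on adherence and Step 3 for attenuation of the time effect before Step 4 is reached. The direct, indirect and total effects and the percentage mediated are reported as well. Simulation noise in the p-value does not bias those estimates.

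Finally, a reader might take the missing number in the cost mediation as a defect. The number of replicates is commonly left to the SAP, which is not at hand, and the cost section states nothing that contradicts the HbA1c section. Aligning the two is a matter of consistency.

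**Conclusion.** The point holds as a minor one. For the HbA1c mediation test, the stated minimum of 500 is low for a yes/no decision at 0.05. At exactly 500 samples, the verdict is sensitive to the seed for a true p of roughly 0.03 to 0.08 if p is a percentile p, or roughly 0.04 to 0.06 if it uses the bootstrap standard error. Outside those bands the decision is stable. The figures assume that the minimum is what is run, and they depend on an unstated p-value method.

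**What to change.** In Step 4 of the HbA1c mediation, raise the minimum from 500 to at least 5,000 bootstrap samples and require a fixed, recorded seed. Apply the same minimum in Step 4 of the cost mediation. A statement of how the p-value is formed, for which the SAP is a natural place, would settle which of the ranges above applies.

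Five thousand brings the percentile standard error below 0.005; 10,000 is a reasonable choice if computing allows. The fixed seed makes the result reproducible but does not remove the noise. Even at 5,000, a true p of 0.045 or 0.055 still lands on the wrong side about 13% of the time under the percentile method, so a p-value that close to 0.05 should be read with that in mind.

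The only cost is computing time. No data, cohort or model changes.

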- ❖ **Primary Objective 1:** Evaluate the treatment patterns of insulin including observed total daily dose [TDD] in claims, adherence, prescription fill rate, claim gaps, persistence and concomitant medication use among T2DM patients before and after U-500R syringe initiation and U-500R Kwikpen initiation separately as well as before and after U-500R device switch from syringe to Kwikpen:
 - Characterize U-500R Kwikpen patients;
 - Determine differences between treatment patterns before and after U-500R Kwikpen initiation;
 - Determine differences between treatment patterns before and after U-500R syringe initiation; and
 - Determine differences between treatment patterns before and after U-500R device switch from syringe to Kwikpen.

Research Objective 2: Treatment Outcomes

- ❖ **Primary Objective 2:** Evaluate the HbA1c level among T2DM patients before and after U-500R syringe initiation and U-500R Kwikpen initiation separately, as well as before and after U-500R device switch from syringe to Kwikpen:
 - Determine differences between HbA1c level before and after U-500R Kwikpen initiation;
 - Determine differences between HbA1c level before and after U-500R syringe initiation;
 - Determine differences between HbA1c level before and after U-500R device switch from syringe to Kwikpen; and
 - Determine whether observed TDD in claims or insulin adherence played a role in HbA1c changes among U-500R syringe initiators, U-500R Kwikpen initiators, and device switchers from syringe to Kwikpen.
- ❖ **Secondary Objective 2a:** Evaluate the hypoglycemic events among T2DM patients before and after U-500R syringe initiation and U-500R Kwikpen initiation separately, as well as before and after U-500R device switch from syringe to Kwikpen:
 - Determine differences between hypoglycemia events before and after U-500R Kwikpen initiation;
 - Determine differences between hypoglycemia events before and after U-500R syringe initiation;

[2018-7241 Study Identifier] Observational Study Protocol

- Determine differences between hypoglycemia events before and after U-500R device switch from syringe to Kwikpen; and
 - Determine whether observed TDD in claims or insulin adherence played a role in hypoglycemic events among U-500R syringe initiators, U-500R Kwikpen initiators, and device switchers from syringe to Kwikpen.

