Zero-inflated negative binomial mixed model will be used to evaluate factors associated with number of hypoglycemia events PPPY in the pre- and post-index periods among U-500R syringe initiators, U-500R Kwikpen initiators, and U-500R device switchers. Zero-inflated negative binomial distribution is a mixture of a binary distribution that is degenerate at zero and an ordinary count distribution such as negative binomial. In cases of outcome variable being repeatedly measured from the individual subjects, zero inflated models are extended to include random effects to account for the correlation among the repeated measures within a subject. In the current model, the number of hypoglycemia events which might have more zeroes (for example not every patient might have a lab visit for glucose) and is measured at two time intervals (before and after the index event; U-500R initiation/device switch), will be considered the dependent variable. Observed TDD, and HbA1c will be considered as the time varying covariates in the model (measured both in the before and after index date), and the time-independent covariates will include the demographic and clinical characteristics.

The complete list of covariates will include:

- age
- sex
- race
- BMI
- baseline CCI score

[2018-7241 Study Identifier] Observational Study Protocol

- observed TDD from claims
- HbA1c
- time (pre/post)

Note: Age, sex, race, BMI, and CCI score will be assessed during pre-index period. Observed TDD and HbA1c will be calculated during the entire pre-index and post-index periods, respectively. Pre-index HbA1c will be defined as the HbA1c measurement -90/+30 days of the index date. For patients with multiple HbA1c measurements within this period, the measurement taken closest to the index event date will be reported as the pre-index HbA1c value. Post-index HbA1c will be defined as the HbA1c within 2 months of the end of the follow-up period.

Research Objective 2: Secondary Objective 2bDescriptive Analysis

Treatment outcomes (HbA1c and number of hypoglycemic events) and prescriber behavior (observed TDD in claims and prescribed TDD from the physician) will be analyzed descriptively and quarterly before and after U-500R syringe initiation and U-500R Kwikpen initiation, and before and after U-500R device switch from syringe to Kwikpen.

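### In the hypoglycemia model, the time and dose coefficients need not equal the effect on events per patient per year; name the overall-mean rate ratio as the Objective 2a result

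*Protocol*

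**What the plan says.** Protocol section 4.1 sets the question under Secondary Objective 2a: "Determine differences between hypoglycemia events before and after U-500R Kwikpen initiation". It asks the same for syringe initiation and device switch, and also asks whether observed TDD played a role. Table 3 reports hypoglycemia as events PPPY in each period, with no restriction to a subgroup of patients.

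Section 6.4.1 (Secondary Objective 2a, Multivariate Analysis) fixes the model: "Zero-inflated negative binomial mixed model will be used to evaluate factors associated with number of hypoglycemia events PPPY in the pre- and post-index periods". It describes the distribution as "a mixture of a binary distribution that is degenerate at zero and an ordinary count distribution such as negative binomial", and adds that "zero inflated models are extended to include random effects to account for the correlation among the repeated measures within a subject". The outcome, it says, "might have more zeroes (for example not every patient might have a lab visit for glucose". On covariates: "Observed TDD, and HbA1c will be considered as the time varying covariates in the model". Time (pre/post) is on the same single list.

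The section does not assign covariates to the count part or the zero part. It names no contrast that combines the two. The same section also plans an unadjusted paired t-test for continuous variables. Section 6.3 sets two-sided p<0.05 without multiplicity adjustment.

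**The concern.** The target is a mean over all patients, whereas the named model estimates two separate quantities. A count-part coefficient is a log rate ratio among records that are not structural zeros. A zero-part coefficient is a log odds ratio for being a structural zero. If time or TDD acts on both, neither coefficient is the effect on PPPY.

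The plan's own explanation of the zeros makes this more than a formality. Under Table 3 a glucose value of 70 mg/dL or below counts as an event, so the zero share depends partly on how often glucose is measured. Testing could well change when a new insulin or device is started, and could vary with dose.

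Hypoglycemia is the only adverse event that section 7.1 defines. If the count-part coefficient is read as the PPPY result at p<0.05, the report could claim a change in the overall rate where there is none, or miss a rise that comes from more patients having events.

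**Working it through.** The Protocol gives no event rate, zero share, dispersion or power for this analysis, so there is no stated figure to reproduce. All zero shares, means, dispersions and sample sizes below are assumptions. Table 4 gives only preliminary VHA counts, before the selection criteria.

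**Step 1: algebra.** With zero share π and count-part mean μ, the overall mean is (1 − π) × μ. Hence

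overall rate ratio for time = exp(β count) × (1 − π post) / (1 − π pre).

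Both periods are 9 months (section 5.4), so PPPY = count × 12/9 in each and the factor cancels. A random intercept in the count part that is independent of the zero part also cancels.

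| π pre → π post | Count-part ratio | Overall ratio |
|---|---|---|
| 0.60 → 0.60 | 1.25 | 1.25 × 0.40/0.40 = 1.25 |
| 0.60 → 0.50 | 1.00 | 1.00 × 0.50/0.40 = 1.25 |
| 0.60 → 0.68 | 1.25 | 1.25 × 0.32/0.40 = 1.00 |
| 0.30 → 0.50 | 1.00 | 1.00 × 0.50/0.70 = 0.714 |

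For these time-only values, the count-part and overall ratios agree only in the first row, where the zero share is constant.

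**Step 2: does the test follow?** Simulation with 1,000 patients per period, pre-index count-part mean 3, dispersion 0.5, independent periods, no random effects, 150 replicates, Wald test at 1.96:

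- Time in both parts, row 2 (overall rise of 25%): the count ratio averages 1.00 and its test rejects in 4%. The zero-part test rejects in 97%.
- Time in both parts, row 3 (no overall change): the count ratio averages 1.25 and its test rejects in 85%.
- Intercept-only zero part, row 1 (constant share): the count ratio averages 1.249 against a true 1.25, with 90% rejection. Here the coefficient does answer the PPPY question.
- Intercept-only zero part, row 2 (share changes): the count ratio averages 1.075 against a true 1.25, with 18% rejection. Dropping covariates from the zero part therefore gives bias rather than a cure.

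**Step 3: sparser events.** Zero share 75% before and 65% after, pre-index count-part mean 3, dispersion 0.8, independent periods.

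- No change: 0.25 × 3 = 0.75 before. After, the count-part mean is 0.75/0.35 = 2.14, so 0.35 × 2.14 = 0.75.
- Rise: 0.35 × 3 = 1.05 after, and 1.05/0.75 = 1.40.

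Rejection rates at 500 / 1,000 patients per period (one range where repeated runs are pooled):

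| Test of time | No change in mean | True 40% rise |
|---|---|---|
| Count part, time in both parts | 65% / 89% | 2% to 10% |
| Count part, intercept-only zero part | 30% / 48% | 11–14% / 20–27% |
| Zero part | not a test of the mean | 77% / 97% |
| Overall rate ratio from both parts of the same fit | 6% / 4% | 53% / 84% |
| Paired t-test, unadjusted | – | 59% / 83% |

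With 150 replicates, simulation error is at most about 1.96 × √(0.25/150) = 0.08. The contrasts are far larger than that.

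**The case against.** The strongest reply is that the Protocol never says the count-part coefficient alone decides. It says only that associated factors will be evaluated. Which part carries which covariate, and whether a combined ratio is derived, may be settled in a statistical analysis plan that is not shown. That stands as far as missing detail goes. It does not remove the mismatch between the model and the target that the Protocol does fix.

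Second, the rise that the count part misses is visible elsewhere: in the zero-part test (77% / 97%), in the paired t-test (59% / 83%) and, if any event is tabulated as yes/no, in McNemar's test (85% / 100%). This stands for the crude before/after change. None of the paired tests adjusts for covariates or addresses TDD.

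Third, the no-change scenario needs the count-part mean to fall from 3 to 2.14 (−29%), exactly cancelling the shift in zeros. Rejection there detects a real change in the count part. That is true, and it is why the example shows a mismatch of questions rather than a faulty test.

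Fourth, if zeros reflect absent testing, separating them is defensible: an overall-mean model may report more hypoglycemia when only testing has increased. This stands, and is a reason to keep both parts in view.

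A reader might infer more than the Protocol supports:

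- That the model never tests PPPY. With a constant zero share it does.
- That it must be replaced. The overall ratio from the same fit holds its size (6% / 4%) and has good power at 1,000 patients per period (84%).
- That the outcome is a non-integer because 1 event / 0.75 year = 1.33. The same paragraph of section 6.4.1 names the number of events as the dependent variable, and the scaling cancels.

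**Conclusion.** The point holds in a conditional form. The count-part coefficient for time or TDD need not equal the effect on PPPY. It does so when the zero share is constant, which the plan's own account of the zeros makes doubtful. An intercept-only zero part is biased if the share changes (1.075 against a true 1.25 in the example).

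Under the assumed inputs, the count-part test can reject in 65% to 89% of trials with unchanged mean events, and in 10% or fewer with a true 40% rise. The consequence is confined to the adjusted time effect and the dose question in Objective 2a, because the crude change has its own paired test.

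The sizes are illustrative: the Protocol supplies none of the inputs, and the simulations omit random effects and within-patient correlation. The algebra does not depend on the assumed values.

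**What to change.** In section 6.4.1, Secondary Objective 2a:

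1. State that the modelled outcome is the integer number of events per period. A log person-time offset may be written in, but it is constant here because both periods are 9 months.
2. Allow time and TDD in both the count part and the zero part.
3. Name the overall-mean rate ratio for time, and for TDD per a stated increment, as the Objective 2a result. Obtain it from both parts of the fitted model, averaged over the observed covariates, or directly from a marginalised zero-inflated negative binomial model.
4. Add a negative binomial GEE with robust standard errors as a sensitivity analysis.
5. Report the separate count-part and zero-part coefficients as supportive, noting that the zero part may reflect glucose testing rather than hypoglycemia.

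The cost is a few sentences and a little more programming, feasible in SAS 9.4 (NLMIXED or GENMOD). No new data are needed.
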